### ***Decision-making algorithm for pravastatin safety/PK study:***

Scenario/Pravastatin Dose	Safe/tolerable?	<math>AUC_{0-24}</math> reduction	Decision
1 40 mg daily	Y	=	Increase dose to prava 80 mg and enroll additional participants
2 40 mg daily	N	=	Enroll 5 additional participants (10 total) and discontinue study

3 80 mg daily	N	=	Discontinue study
4 80 mg daily	Y	< 40%	Discontinue study
5 80 mg daily	Y	≥ 40%	Increase dose to prava 120 mg and enroll additional participants
6 120 mg daily	N	=	Discontinue study
7 120 mg daily	Y	<40%	Discontinue study
8 120 mg daily	Y	≥ 40%	Increase dose to prava 160 mg and enroll additional participants
9 160 mg daily	N	=	Discontinue study
10 160 mg daily	Y	=	Study complete

Safety/tolerability: Y= Yes; <3 participants with  $\geq$  one grade 3 (or higher) event of musculoskeletal symptoms, creatine kinase elevation, or liver function test elevation attributed to study drug (probable or definite)

N= No; For Arm 1 (pravastatin 40 mg daily):  $\geq$  1 participant with  $\geq$  one grade 3 (or higher) event of musculoskeletal symptoms, creatine kinase elevation, or liver function test elevation attributed to study statin medication (probable or definite).

For Arms 2, 3, and 4:  $\geq$  3 participants with  $\geq$  one grade 3 (or higher) event of musculoskeletal symptoms, creatine kinase elevation, or liver function test elevation attributed to study statin medication (probable or definite)

$AUC_{0-24}$ = Area-under-the-plasma-concentration-time curve for 24-hour exposure

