#### Creatinine Kinase Elevation

For Grade 1 (3 to  $< 6 \times$  ULN) or Grade 2 (6 to  $< 10 \times$  ULN) creatinine kinase elevation, participants may continue study drug treatment and should be carefully evaluated and followed closely. For Grade 3 (10 to  $< 20 \times$  ULN) or higher creatinine kinase elevation, participants will permanently discontinue statin but will be requested to attend follow-up visits until study end.

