***Sample size***

The sample size will be between 5 and 35 evaluable participants, who will be recruited into the following arms: 1) Standard-of-care regimen (Rifafour) + pravastatin 40 mg daily (5 evaluable participants); 2) Standard-of-care regimen (Rifafour) + pravastatin 80 mg daily (10 evaluable participants); 3) Standard-of-care regimen (Rifafour) + pravastatin 120 mg daily (10 evaluable participants); 3) Standard-of-care regimen (Rifafour) + pravastatin 160 mg daily (10 evaluable participants). Participants in Arms 2, 3, and 4 (10 participants each) will only be recruited if necessary, i.e., if pravastatin 40 mg is well tolerated and safe, and if escalated doses are also tolerated and safe, yet drug exposures are reduced by  $\geq 40\%$  in participants due to the known interaction with rifampin.

A sample size of 10 evaluable participants for pravastatin PK analysis was chosen based on within-subject variability (CV%) of statin AUC in interaction studies ranging from 6-60% and a within-subject coefficient of variation (CVw) of 33%. With 10 evaluable participants per arm, the precision (i.e., half width of the 90% confidence interval on the log scale) for the treatment difference will be within 26% of the point estimate for AUC. If the point estimate of the ratio of geometric mean is 1, then 90% confidence interval will be approximately (0.74, 1.35).

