## ***Data Analysis***

The current study is a 2-week, 4-arm dose-escalation trial to determine the safety/tolerability and PK of pravastatin when co-administered with the standard drug regimen for drug-susceptible TB (Rifafour). Participants will receive standard anti-TB therapy and pravastatin beginning at a dose of 40 mg once daily. Each subsequent arm (pravastatin 80 mg, 120 mg, and 160 mg) of this study will continue to recruit participants until at least 10 participants in each group are evaluable for full PK analysis.

The primary endpoints in this study are safety/tolerability and pravastatin exposures. A regimen will be deemed safe and well tolerated if none of the participants require treatment discontinuation for a pravastatin-related adverse reaction and  $\leq 3$  participants experience a pravastatin-related grade 3 (or higher) adverse event during the 14-day study period and follow up. PK parameters (e.g., area under the concentration-time curve over 24 hours ( $AUC_{0-24}$ ), minimum concentration ( $C_{min}$ ), maximum concentration ( $C_{max}$ ), and oral clearance (Cl/F)), will be estimated for pravastatin from intensive sampling data after a single dose of pravastatin (baseline PK, prior to initiation of TB treatment) and after 14 days of co-administration with the first-line anti-TB regimen. Based on PK data of pravastatin when co-administered with rifampin ( $T_{max} = 1$  hour,  $T_{1/2} = 1.5$  hours), plasma samples will be collected for pravastatin measurements by LC-MS/MS at the following time points: pre-dose, 0.5 hrs, 1 hr, 1.5 hrs, 2 hrs, 3 hrs, 4 hrs, 6 hrs, and 8 hrs. Pravastatin exposures will be calculated using a noncompartmental approach using standard PK software, e.g., Phoenix WinNonLin. Using all PK data, a PK/PD model will be developed to evaluate the relationship between drug exposures (e.g.,  $C_{max}$ ,  $T_{max}$  or  $AUC_{0-24}$ ) and outcomes (e.g., safety/tolerability).  $C_{max}$  and  $t_{max}$  will be taken directly from the original data. The terminal log-linear phase of the plasma concentration-time curve will be identified visually for each curve.

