#### ***Decision-making algorithm for initiating new dosing cohorts***

The study will be monitored by a DSMB, which will review the safety data for each cohort and will give approval before initiation of each possible dose escalation. Specifically, study drug dose will not be escalated and the study if any three participants develop grade 3 or higher musculoskeletal/CK-related adverse events (AEs), LFT-related AEs ( $> 5 \times UNL$  without symptoms, but  $> 3 \times UNL$  with symptoms or bilirubin  $> 2 \times ULN$ ) or any type of grade 4 event regardless of causal attribution. Study drug dosage will be escalated only if the dose is deemed safe/tolerable based on the above rules and the mean pravastatin AUC is reduced by  $\geq 40\%$  relative to the pre-Rifafour value. Study participants in whom the study drug has been discontinued will remain in the study until the final clinical visit and laboratory evaluation. In the event of study product discontinuation, management of the standard-of-care TB drugs will revert to the site clinician as per national guidelines.

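### The rules for the 40-to-80 mg step conflict: one section adds a 40% AUC condition that others omit, and one or two events in five count as both safe and not safe

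*Combined protocol and SAP*

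**What the plan says.** **Exposure condition for 40 to 80 mg.** Row 1 of the table in Section 18 (Decision-making algorithm for pravastatin safety/PK study) raises a safe 40 mg arm to 80 mg. It gives no AUC threshold, unlike rows 4, 5, 7 and 8. Section 15 also makes the 80 mg cohort follow from tolerability at 40 mg, and the Abstract attaches an exposure condition only to Arms 3 and 4. The next part of Section 18 (Decision-making algorithm for initiating new dosing cohorts) says the dose will be "escalated only if the dose is deemed safe/tolerable based on the above rules and the mean pravastatin AUC is reduced by" 40% or more, and excepts no dose. The Sample size section says "Participants in Arms 2, 3, and 4 (10 participants each) will only be recruited if necessary", then gives a condition that runs together safety at 40 mg, safety of escalated doses and a reduction of at least 40%.

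**Safety condition.** Under the table, the safe entry reads "Y= Yes; <3 participants with" a qualifying grade 3 or higher event and names no arm. The other entry opens "N= No; For Arm 1 (pravastatin 40 mg daily" and is met by one participant; for Arms 2-4 it takes three. The new-cohorts section bars escalation when any three participants have events and sets no lower figure for Arm 1. Data Analysis has a further definition: "A regimen will be deemed safe and well tolerated if none of the participants require treatment discontinuation for a pravastatin-related adverse reaction" and no more than 3 have a related grade 3 or higher event.

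**If 40 mg is not safe.** Row 2 reads "Enroll 5 additional participants (10 total) and discontinue study". The DSMB "will give approval before initiation of each possible dose escalation".

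**The concern.** These are the rules that site staff and the DSMB apply at the first decision point. A safe 40 mg arm with an AUC reduction under 40% goes to 80 mg by the table and may not be escalated by the new-cohorts section. Taken literally, the second rule would block 80 mg, the dose whose expected exposure defines the primary endpoint in the Abstract. With one or two qualifying events in five, the table both escalates and does not, and that is the safety threshold for the first cohort.

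The 40% cut also sits in the middle of the 30-50% reduction that the protocol expects (Section 13, Drug-drug interactions), so the exposure conflict is likely to arise in practice.

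**Working it through.** **1. The plan's own precision figure.** Sample size gives n = 10, within-subject CV 33% and a 90% log-scale half-width of 26%. With σ = √ln(1 + 0.33²) = 0.3215, the half-width is t(0.95, 9 df) × σ × √(2/10) = 0.264, which reproduces the 26%. (The antilog interval is 0.77-1.30; the plan prints 0.74-1.35. Nothing below depends on this.) The same paired log-normal model is used next.

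**2. How often the two exposure rules disagree.** At n = 5 the SD of the mean log ratio is 0.3215 × √(2/5) = 0.2033. If the true ratio is R, the chance that the observed reduction is below 40% is Φ[(ln R − ln 0.6)/SD].

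| True reduction | CV 33% (SD 0.2033) | CV 60% (SD 0.3507) | CV 6% (SD 0.0379) |
|---|---|---|---|
| 30% (R = 0.7) | 78% | 67% | about 100% |
| 40% (R = 0.6) | 50% | 50% | 50% |
| 50% (R = 0.5) | 19% | 30% | about 0% |

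The outer columns use the ends of the 6-60% range in Sample size. The plan does not say which mean its rule uses; the geometric mean is assumed here.

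**3. Which rule fits the aim.** Section 13 states that AUC is proportional to dose. At 40 mg with a fractional reduction r, exposure is therefore 0.5 × (1 − r) of that from 80 mg alone. With r between 0 and 40%, that is 50% down to 30% of the target. A 40 mg arm that misses the 40% cut is still well short of the target, so holding the dose there would not serve the stated aim. This supports safety alone as the intended rule for this step.

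**4. The safety rules in Arm 1 (n = 5).**

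| Participants with a qualifying event | Decision table | Three-participant bar, new-cohorts section |
|---|---|---|
| 0 | Y | not reached |
| 1 or 2 | Y and N | not reached |
| 3 to 5 | N | reached |

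P(1 or 2 of 5) = 5p(1−p)⁴ + 10p²(1−p)³ = 4.9%, 22.5%, 40.1% and 61.4% at p = 1%, 5%, 10% and 20%. These rates are assumptions, because the documents give none for the combined trigger. The CK counts in Section 13, Tolerability (4/464 at 80 mg, 0/115 at 40 mg) cover CK only and come from a mean exposure of 8.6 months, so they do not supply it.

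**5. Data Analysis against the table.** Section 5 says that for grade 3 "or higher creatinine kinase elevation, participants will permanently discontinue statin", and ALT above 5 × ULN also ends treatment. One statin-related event of either kind therefore fails Data Analysis in any arm, yet passes the table in Arms 2-4, where up to two are allowed. In the other direction, exactly three participants with related grade 3 events meet the Data Analysis count (≤3) but fail the table (<3).

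**6. Totals.** 5 + 10 + 10 + 10 = 35, which agrees with the Abstract and Sample size. Recruitment strategy gives 10 to 30.

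**The case against.** The best reply is that the intent is clear. Three specific statements (row 1, Section 15, the Abstract) outweigh one general sentence. For one or two events in Arm 1, N is evidently meant: that rule is the specific one, and the discontinuation clause in Data Analysis points the same way. The DSMB would sort it out.

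The argument about intent stands, and the fix follows it. It does not remove the conflict. The general sentence sits in the section that governs new cohorts and is worded as a necessary condition, and the three-participant bar there supports the opposite reading for Arm 1. DSMB approval does not tell the DSMB which rule the protocol sets.

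Two stronger readings are tempting and are not supported:

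- *That row 2 is a mistake that exposes five more people for nothing.* The Abstract allows 5-10 per arm and fixes Arm 1 at five only if well tolerated, so the expansion looks deliberate. Data Analysis puts all PK data into an exposure-outcome model, and the study is meant to inform later dose selection. The risk is limited: 40 mg is the recommended starting dose, rifampin is expected to lower exposure, individual stopping rules apply, and the DSMB reviews each cohort and can decide on early stopping. What remains is that no escalation decision uses these five, no purpose is stated for them, and DSMB approval is tied to escalation rather than to dosing them.
- *That Sample size also requires the AUC reduction before 80 mg.* Its clause can attach to the escalated doses only, so that section is ambiguous. The conflict rests on the new-cohorts section. Nor does it rest on the symbol in row 1's AUC cell, which may be an extraction artefact.

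**Conclusion.** The concern holds in two parts. First, the new-cohorts section conflicts with row 1, Section 15 and the Abstract on whether 40 to 80 mg needs an AUC reduction of at least 40%. For a safe arm of five the rules would disagree with probability about 78%, 50% and 19% at true reductions of 30%, 40% and 50%, assuming CV 33%, a paired log-normal analysis and the geometric mean ratio. Second, the Arm 1 Y and N rules overlap at one or two events in five, and Section 18 holds two further safety rules that do not match the table.

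The probabilities are not the chance that the study is wrongly halted. They apply only if the 40 mg arm is safe, and harm follows only if the general sentence is preferred to row 1. A reader might also infer that the study would then end at five participants. The new-cohorts section says only that the dose is not escalated. The stated minimum of 5 would fit such a stop, but it would equally fit a DSMB stop.

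This should be fixed before the first cohort is reviewed. The row 2 expansion is a secondary point, and the 10-30 range is clerical.

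**What to change.** - New-cohorts section: state that the ≥40% AUC condition applies to escalation from 80 mg upward and that 40 to 80 mg rests on safety alone. Clarify Sample size to match.
- Decision table: define Y for Arm 1 as 0 participants with a qualifying event, and label the fewer-than-3 rule as Arms 2-4.
- New-cohorts section: amend the three-participant bar so that it is 1 for Arm 1.
- Data Analysis: align with the table's thresholds, covering both the count and the discontinuation clause, so that one safety rule applies in each arm.
- Row 2: if the expansion is kept, state its purpose and require DSMB review before the extra five are dosed.
- Recruitment strategy: replace 10-30 with a range whose maximum is 35. The minimum should follow from the final rules: by the table alone it is 10 (row 2) or 15 (row 1, then 80 mg), against the 5 in Sample size.

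The cost is wording, plus one DSMB review if row 2 is reached. Stopping at five in row 2 is an alternative but loses information. The 90% interval around an AUC ratio of 1 would be about 0.65-1.54 at n = 5 (half-width t(0.95, 4 df) × 0.2033 = 0.433) against 0.77-1.30 at n = 10. That is a trade-off for the sponsor and not a required correction.

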### ***Severity\****

With the exception of creatinine kinase elevation, all symptoms and laboratory findings will be graded according to severity using the Division of AIDS Table for Grading Severity of Adult and Pediatric Adverse Events, Corrected Version 2.1, July 2017, which, in our view is the most comprehensive grading scale for patients with infectious diseases, including TB or HIV.

The protocol-specific criteria for grading elevated CK are as follows:

PARAMETER	GRADE 1 MILD	GRADE 2 MODERATE	GRADE 3 SEVERE	GRADE 4 POTENTIALLY LIFE-THREATENING
Creatinine kinase, high	3 to < 6 x ULN	6 to < 10 x ULN	10 to < 20 x ULN	> 20 x ULN

The DAIDS toxicity table criteria for grading liver function tests are as follows:

PARAMETER	GRADE 1 MILD	GRADE 2 MODERATE	GRADE 3 SEVERE	GRADE 4 POTENTIALLY LIFE-THREATENING
AST or SGOT, High	1.25 to < 2.5 x ULN	2.5 to < 5.0 x ULN	5.0 to < 10.0 x ULN	≥ 10.0 x ULN
ALT or SGPT, High	1.25 to < 2.5 x ULN	2.5 to < 5.0 x ULN	5.0 to < 10.0 x ULN	≥ 10.0 x ULN
Total bilirubin	1.1 to < 1.6 x ULN	1.6 to < 2.6 x ULN	2.6 to < 5.0 x ULN	≥ 5.0 x ULN

\*The DAIDS AE Grading Table is available at: <https://rsc.niaid.nih.gov/clinical-research-sites/daids-adverse-event-grading-tables>.

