### ***Clinical Management of Adverse Events***

#### Liver toxicity

Study treatment will be permanently discontinued if any of the following criteria are met:

- ALT > 5x the upper limit of normal (ULN) without symptoms
- ALT > 3x ULN with signs or symptoms suggestive of clinical hepatitis including one or more of the following: nausea, vomiting, abdominal pain, dark colored urine or clay colored stools, unexplained fever, jaundice, liver tenderness, or hepatomegaly
- ALT > 3x ULN and Total Bilirubin  $\geq$  2x ULN

If a patient develops hepatic toxicity meeting the above stopping criteria, the following evaluation will be undertaken: assessment for history of injection or non-injection drug use, alcohol ingestion, use of other hepatotoxic drugs, and performance of serologic tests for viral hepatitis (IgM antibody for Hepatitis A, Hepatitis B surface antigen, IgM antibody to Hepatitis B core antigen, antibody to Hepatitis C). In addition, an AST and INR should also be checked, if not already done.

Participants will be followed until resolution (return to baseline) or stabilization of the ALT elevation.

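### A pravastatin-attributed liver stop that is only grade 2 counts as zero in the dose-escalation table, so one such stop in Arm 1 reads as escalate to 80 mg

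*Combined protocol and SAP*

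**What the plan says.** Five parts of the combined protocol and SAP bear on this.

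- **Section 5, Liver toxicity.** "Study treatment will be permanently discontinued if any of the following criteria are met". Two of the three criteria begin below 5x ULN: "ALT > 3x ULN with signs or symptoms suggestive of clinical hepatitis including one or more of the following" (a symptom list follows), and "ALT > 3x ULN and Total Bilirubin" at or above 2x ULN. The third is ALT above 5x ULN without symptoms.
- **Section 5, Severity.** ALT or AST of "2.5 to < 5.0 x ULN" is grade 2. Total bilirubin of "1.6 to < 2.6 x ULN" is grade 2.
- **Section 18, decision table for the safety/PK study.** The counted event is a "grade 3 (or higher) event of musculoskeletal symptoms, creatine kinase elevation, or liver function test elevation attributed to study drug (probable or definite"). Y is fewer than three participants, with no arm named. N is one or more participants in Arm 1 and three or more in Arms 2 to 4. At 40 mg, Y leads to "Increase dose to prava 80 mg and enroll additional participants".
- **Section 18, Data Analysis.** A regimen is safe only if nobody has to stop treatment for a pravastatin-related reaction. A limit on grade 3 events applies as well.
- **Section 18, initiating new dosing cohorts.** The dose is not raised "if any three participants develop grade 3 or higher musculoskeletal/CK-related adverse events (AEs), LFT-related AEs". Its liver bracket includes values above 3x ULN with symptoms or with bilirubin above 2x ULN. Escalation also requires the dose to be safe under the rules set out above it, which are not named, and DSMB approval.

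**The concern.** The stopping rule and the escalation table use different liver thresholds. A participant can be taken off treatment permanently for suspected drug-induced hepatitis and still be invisible to the table that decides on the next dose, because the laboratory values are grade 2.

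This matters most in Arm 1. Section 15 explains that the five-person 40 mg cohort was added because the effect of giving pravastatin with isoniazid, ethambutol and pyrazinamide is unknown. The table's N definition lets a single grade 3 liver event fail that arm. A liver event serious enough to end treatment should not count for less than that, yet it counts for nothing. The DSMB would then hold a table that points to doubling the dose and a Data Analysis definition that calls the same dose not safe.

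**Working it through.** The plan gives no figure of its own here. The check is of rule logic, followed by a size calculation under assumed rates.

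**1. Where a stop falls below grade 3.**
- ALT: the stop starts above 3x ULN and grade 3 starts at 5.0x. The overlap with grade 2 is >3 to <5x.
- Bilirubin, for the route without symptoms: the stop needs at least 2x ULN and grade 3 starts at 2.6x. The overlap is 2.0 to <2.6x.
- For a zero count, AST must also be below 5x ULN and bilirubin below 2.6x on either route, because a grade 3 value of either is itself a counted liver test elevation.

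**2. Example profiles** (multiples of ULN; AST below 5x in every row; attributed to pravastatin at the level the table requires).

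| ALT | Bilirubin | Symptoms | Section 5 stop | Table now | Cohort rule | Table after fix |
|---|---|---|---|---|---|---|
| 4 (AST 3) | 1.0 | nausea | yes | 0 | 1 | 1 |
| 4 (AST 3) | 2.3 | none | yes | 0 | 1 | 1 |
| 3.1 | 2.0 | none | yes | 0 | 0 | 1 |
| 4 | 2.6 | none | yes | 1 | 1 | 1 |

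The third row is missed by the cohort rule as well, because that rule says above 2x where section 5 says at or above 2x.

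**3. One stop of the first kind in Arm 1.**
- Table: 0 counted, so Y, which means go to 80 mg.
- Cohort rule: 1 of 3, so not blocked.
- Data Analysis: one pravastatin-related discontinuation where none is allowed, so not safe.

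**4. The Y and N definitions overlap in Arm 1.** Y (fewer than three) names no arm, and N for Arm 1 is one or more. With one or two counted participants, Arm 1 meets both. If only the liver item were reworded, the stop in step 3 would count 1 and still satisfy Y as written. Y therefore has to be split by arm.

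**5. Size.** With an assumed probability p of such a stop per participant, independent across five participants, P(at least one) = 1 − (1 − p)^5:
- p = 0.01: 1 − 0.951 = 0.049
- p = 0.02: 1 − 0.904 = 0.096
- p = 0.05: 1 − 0.774 = 0.226

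**6. Arms 2 to 4 (n = 10), same three rates.**
- At least three such stops, the table's limit after the fix: 0.0001, 0.0009, 0.0115.
- At least one, the Data Analysis limit: 1 − (1 − p)^10 = 0.096, 0.183, 0.401.

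The two limits differ greatly, so choosing between them is a design decision.

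**The case against.** The strongest reply is that the table does not act alone. The cohort section makes safety under the preceding rules a necessary condition for escalation. It follows both Data Analysis and the table, and its language of a dose being deemed safe echoes Data Analysis. On that reading the Arm 1 example is blocked. The DSMB reviews each cohort and must approve each step (section 4, Safety Evaluation; section 18), and Early stopping rules lets it act on the frequency or severity of events. This stands as a real limit on harm. A reader might infer that the protocol would drive the dose up after such a stop. The documents do not support that. They show a table with the wrong answer, inside a process that may well catch it.

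A second reply is that the window is narrow and the events are probably uncommon. Section 13 reports no excess of liver function abnormalities with 40 mg pravastatin, and events attributed only to the TB drugs do not count in the table or in Data Analysis. This also stands. The rates used above are assumptions and do not show that such stops are common.

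A third reply is that grade 3 was a deliberate choice. This is weaker, because the cohort section already lists liver criteria that begin above 3x ULN, so the plan treats them as relevant to escalation.

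**Conclusion.** The point holds in a limited form. The table counts zero for a pravastatin-attributed permanent stop with ALT >3 to <5x ULN plus hepatitis symptoms, or plus bilirubin 2.0 to <2.6x ULN, provided AST is below 5x and bilirubin below 2.6x. For one such stop in Arm 1 the table says escalate, the cohort rule does not block, and Data Analysis says not safe. The table's Y and N definitions also overlap in Arm 1.

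The logic rests only on the stated thresholds and on the event being attributed to pravastatin as the table requires. The probabilities of 4.9%, 9.6% and 22.6% rest on assumed rates of 1%, 2% and 5%.

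A reader might also infer that the zero-discontinuation limit in Data Analysis should be made binding in every arm. The documents do not settle this. Section 5 turns most grade 3 liver and CK events into discontinuations, so a zero limit would leave the table's three-participant threshold in Arms 2 to 4 with almost no effect. Whether zero or fewer than three governs there is for the sponsor to decide.

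**What to change.** 1. In the Y and N definitions of the decision table, replace the liver item with: *grade 3 or higher liver function test elevation, OR any liver event meeting a stopping criterion in Liver toxicity (section 5)*. Keep the attribution wording. The OR preserves isolated grade 3 findings that are not section 5 stops, such as AST 6x with ALT 2.9x, or bilirubin 3x with ALT 1x.
2. Split Y by arm: *Arm 1, zero participants; Arms 2 to 4, fewer than three participants*.
3. In the cohort-initiation section, change the bilirubin criterion from above 2x to at or above 2x ULN, to match section 5.

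Do not impose the zero-discontinuation limit on Arms 2 to 4 as part of this change.

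The cost is wording in two places in section 18. No visits, tests or data are added, because section 5 (Reporting) already requires discontinuations due to adverse events to be reported. The downside is that Arm 1 fails more easily: these events would fail it with the probabilities in step 5 of the working, against none under the table now. If Data Analysis is already binding, those events already fail Arm 1 and the change there adds no further failures.

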### ***Relationship of AE to Study***

The relationship of each adverse event (AE) to the study procedures will be characterized. The PI will make this determination and will classify AEs as related or unrelated. “Related” will mean that there is a reasonable possibility that the AE may be related to the study agent(s). “Not Related” will mean that there is not a reasonable possibility that the AE is related to the study agent(s). When a SAE is assessed as “not related” to study agent(s), an alternative etiology, diagnosis, or explanation for the SAE should be provided. If new information becomes available, the relationship assessment of any AE should be reviewed again and

updated, as required. The study drug (pravastatin) and standard-of-care regimen, Rifafour (isoniazid, rifampin, pyrazinamide, ethambutol) will be assessed for relationship with the AE.

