### ***Association and Attribution/causality***

An adverse event is considered associated with the use of the drug (Adverse Drug Reaction) if the attribution is possible, probable or definite.

The following definitions for rating attribution/causality will be:

Relatedness Rating	Definition
Not Related	There is not a reasonable possibility that the AE is related to the study agent (pravastatin) or Rifafour (isoniazid, rifampin, pyrazinamide, ethambutol)

Related	There is a reasonable possibility that the AE may be related to the study agent (pravastatin) or one or more components of Rifafour (isoniazid, rifampin, pyrazinamide and ethambutol)
---------	--

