#### Other toxicities

Grade 1 toxicities: In general, for grade 1 toxicities, the patient will be followed carefully, and the study drugs will be continued.

Grade 2 toxicities: For grade 2 toxicities, the patient will be followed more carefully, with additional laboratory and/or clinic visits as necessary, and the study drugs temporarily held at the investigator's discretion.

Grade 3 toxicities: For any grade 3 toxicity involving creatinine kinase elevation, with or without myopathy, myalgias, hepatitis, nausea/vomiting, and/or diarrhea, that, in the principal investigator's judgment is due to study drug, the study drug will be discontinued. The clinician should rule out other possible causes of the symptoms before discontinuing study medication. When possible, concomitant medications should be held first at the discretion of the principal investigator if he/she suspects they are contributing to the toxicity. In the event of study product discontinuation, management of the standard of care TB drugs will revert to the site clinician as per local practice.

Grade 4 toxicities: Any patient with grade 4 renal, hepatic, cardiac or hematological toxicity will be immediately discontinued from study therapy. The laboratory test or clinical finding in question will be reassessed as soon as possible. The repeat test will guide management of the event as follows:

- If the repeat assessment shows toxicity of grade 3 or lower, and if the patient has continued to receive study drugs between the two testing dates, then the patient will be managed according to the appropriate toxicity level of the repeat test.
- If the repeat test shows toxicity of grade 3 or lower, and if the participant has not received study drugs between the two testing dates, then the participant will be managed at the discretion of the investigator with regard to the re-administration of study drugs, and otherwise according to the toxicity level of the repeat test.
- If the repeat test shows grade 4 toxicity, then the participant will be permanently discontinued from study medications. Further treatment of TB will be directed by the investigator on an individualized basis. The participant will continue to be followed for study monitoring purposes (as are other participants who make a permanent departure).

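### The escalation rule counts events graded probable or definite, but the plan rates causality only as Related or Not Related; the effect falls mainly on the 40 mg arm

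*Combined protocol and SAP*

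**What the plan says.** **The rule.** In section 18, under the decision-making algorithm for the safety/PK study, a dose is safe if fewer than 3 participants have a grade 3 or higher "event of musculoskeletal symptoms, creatine kinase elevation, or liver function test elevation attributed to study drug (probable or definite"). This safe (Y) definition names no arm. The not-safe (N) definition uses the same attribution level and is arm-specific: at least 1 participant in Arm 1, at least 3 in Arms 2-4. At 40 mg, Y leads to 80 mg (scenario 1). N leads to enrolling 5 more participants and discontinuing the study (scenario 2).

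**The rating.** Section 5, Relationship of AE to Study, states: "The PI will make this determination and will classify AEs as related or unrelated". The bar for the first label is only a reasonable possibility of a link to the study agents. The section adds that pravastatin and Rifafour will both be assessed. The table under Association and Attribution/causality has the same two levels and defines Related as: "There is a reasonable possibility that the AE may be related to the study agent (pravastatin) or one or more components of Rifafour". The sentence above that table calls an event drug-associated "if the attribution is possible, probable or definite", but no definition of those three grades follows.

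**The separate stop.** Section 18, on initiating new dosing cohorts, bars escalation once any three participants have grade 3 or higher musculoskeletal/CK events, liver-test events, or any grade 4 event. It also requires the dose to be safe under the preceding rules, and DSMB approval.

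**The concern.** An escalation criterion should be computable from the data that the plan says will be collected. Here the criterion needs a distinction between possible and probable that the rating scale does not make. The one sentence naming finer grades does not help. It defines none of them, and its cut-point includes possible, which the algorithm leaves out.

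The foreseeable hard case is a grade 3 ALT rise on combined treatment. Section 13 reports asymptomatic aminotransferase elevation in 10-20% of people on isoniazid and names hepatotoxicity as pyrazinamide's most common serious side effect. Such an event could fairly be rated Related to pravastatin and yet be only possibly due to it. Whether it counts would then be settled after the event is known, in an open-label study. In Arm 1 that choice decides between moving to 80 mg and ending the study.

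**Working it through.** No stated figure in the plan bears on this point, so there is none to reproduce. The check is a comparison of text, followed by a count of which outcomes depend on the reading.

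**Step 1: the scales side by side.**

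| Place | Levels | Cut-point |
|---|---|---|
| Sec. 5, Relationship of AE to Study | related / unrelated | reasonable possibility |
| Sec. 5, Association and Attribution, table | Not Related / Related | reasonable possibility |
| Same section, opening sentence | possible, probable, definite (undefined) | possible or higher |
| Sec. 5, Reporting | relationship to study drugs (levels not given) | none |
| Sec. 18, algorithm | probable, definite | probable or higher |

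Nothing maps Related to probable or definite.

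**Step 2: which outcomes change.** Let k be the number of participants in an arm with a listed grade 3+ event that is Related to pravastatin but only possibly due to it. Assume no probable or definite event in that arm.

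| Arm | k | If counted | If not counted | Three-participant stop |
|---|---|---|---|---|
| 1 (n=5) | 0 | Y | Y | not reached |
| 1 | 1 or 2 | N (≥1), and also Y (<3) | Y | not reached |
| 1 | 3 to 5 | N | Y | bars escalation |
| 2-4 (n=10) | 0 to 2 | Y | Y | not reached |
| 2-4 | 3 or more | N | Y | bars escalation |

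The escalation decision depends on the attribution grade only in Arm 1 with k = 1 or 2. The same row shows the overlap between Y and N, which would exist under any attribution scale.

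**Step 3: scale for Arm 1.** The documents give no value for q, the per-participant probability of such an event; 1%, 2% and 5% are assumptions.

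P(at least one of 5) = 1 − (1 − q)^5:
- q = 0.01: 1 − 0.99^5 = 0.0490
- q = 0.02: 1 − 0.98^5 = 0.0961
- q = 0.05: 1 − 0.95^5 = 0.2262

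Removing k ≥ 3, where the separate stop applies anyway, changes little. At q = 0.05, P(k = 1 or 2) = 5(0.05)(0.95^4) + 10(0.05^2)(0.95^3) = 0.2036 + 0.0214 = 0.2250.

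**Step 4: scale for Arms 2-4.** P(three or more of 10) = 1 − Σ C(10,k) q^k (1 − q)^(10−k) over k = 0 to 2, which gives 0.000114, 0.000864 and 0.0115. Even then only the safe/not-safe label differs, because the three-participant stop already bars escalation.

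**The case against.** The best defence is that the three-participant stop carries no relatedness condition for musculoskeletal, CK or liver events, and that the DSMB reviews every cohort with treatment known. The phrase setting causality aside may apply only to grade 4 events, but no attribution is attached to the other items either. This stands for Arms 2-4. It does not protect Arm 1, where one participant decides. The DSMB's approval is a real safeguard, but the plan gives it no rule for converting one scale into the other.

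A second defence is that Arm 1's own N line naturally overrides the general Y line. That is the sensible reading, but the text does not say so.

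Four stronger readings are tempting and are not supported.
- *The rule cannot be applied, or its count is always zero.* An investigator or the DSMB could still judge an event probable or definite. The AE form is not in the documents, so the levels it records are unknown.
- *Rifafour-only events would count.* The table pools the products, but section 5 says both are assessed and the N lines name the statin.
- *The Data Analysis criterion has the same defect.* That criterion speaks of pravastatin-related events, which fits the two-level scale applied to pravastatin.
- *A label alone decides because discontinuation is forced whatever the cause.* The liver section does say "Study treatment will be permanently discontinued if any of the following criteria are met", and the CK section says that for grade 3 "or higher creatinine kinase elevation, participants will permanently discontinue statin". But Other toxicities conditions grade 3 CK elevation and hepatitis on events that in the principal investigator's "judgment is due to study drug, the study drug will be discontinued", and the myopathy section exempts CK rises from exercise or another cause.

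**Conclusion.** The mismatch is real and can be read directly from the text: the algorithm needs a grade of attribution that the defined rating scale does not supply. Its reach is narrow. It can change the escalation decision in Arm 1 when one or two participants have an ambiguous listed event. In the same arm the Y and N definitions contradict each other for one or two counted participants. In Arms 2-4 the grade is largely moot.

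The size rests on an assumed event rate: between 4.9% and 22.6% for at least one such event in Arm 1 as the rate goes from 1% to 5%, given no clearly attributable event. The section 13 hepatotoxicity figures are not rates of grade 3 events over this follow-up and should not be used for q. The safety consequence of a mistaken escalation from Arm 1 is bounded, because 80 mg is still a recommended dose (section 13, Dosage). The larger loss would be stopping, or not stopping, the study on a threshold chosen after the event.

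**What to change.** Before the Arm 1 cohort review:
1. State in section 5 that relatedness is recorded separately for pravastatin and for Rifafour.
2. In the section 18 algorithm, replace the probable-or-definite condition with Related to pravastatin, on the section 5 scale.
3. Delete the leftover sentence naming possible, probable and definite under Association and Attribution/causality.
4. Limit the Y definition of fewer than 3 participants to Arms 2-4, and state 0 participants for Arm 1.

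The cost is a wording amendment and, if the AE form does not already separate the products, one extra field. It adds no visits and does not change the planned arm sizes. The price is a more conservative threshold: compared with counting only probable or definite events, Arm 1 becomes more likely to stop, by about the Step 3 probabilities under the same assumptions. That is slight if ambiguous events are rare and not slight at 5%, so it should be recorded as a deliberate design choice.
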